10.3.1 Definition of AE

AE definition

- An AE is any untoward medical occurrence in a clinical study participant, temporally associated with the use of study intervention, whether or not considered related to the study intervention.
- NOTE: An AE can therefore be any unfavorable and unintended sign (including an abnormal laboratory finding), symptom, or disease (new or exacerbated) temporally associated with the use of a study intervention.
- NOTE: For purposes of AE definition, study intervention (also referred to as Sponsor's product) includes any pharmaceutical product, biological product, vaccine, diagnostic agent, or protocol specified procedure whether investigational or marketed (including placebo, active comparator product, or run-in intervention), manufactured by, licensed by, provided by, or distributed by the Sponsor for human use in this study.

Events meeting the AE definition

- Any abnormal laboratory test results (hematology, clinical chemistry, or urinalysis) or other safety assessments (eg, ECG, radiological scans, vital signs measurements), including those that worsen from baseline, considered clinically significant in the medical and scientific judgment of the investigator.
- Exacerbation of a chronic or intermittent pre-existing condition including either an increase in frequency and/or intensity of the condition.
- New conditions detected or diagnosed after study intervention administration even though it may have been present before the start of the study.
- Signs, symptoms, or the clinical sequelae of a suspected drug-drug interaction.
- Signs, symptoms, or the clinical sequelae of a suspected overdose of either study intervention or a concomitant medication.
- For all reports of overdose (whether accidental or intentional) with an associated AE, the AE term should reflect the clinical symptoms or abnormal test result. An overdose without any associated clinical symptoms or abnormal laboratory results is reported using the terminology "accidental or intentional overdose without adverse effect."
- Any new cancer or progression of existing cancer.

Events NOT meeting the AE definition

- Medical or surgical procedure (eg, endoscopy, appendectomy): the condition that leads to the procedure is the AE.
- Situations in which an untoward medical occurrence did not occur (social and/or convenience admission to a hospital).
- Anticipated day-to-day fluctuations of pre-existing disease(s) or condition(s) present or detected at the start of the study that do not worsen.
- Surgery planned prior to informed consent to treat a pre-existing condition that has not worsened.
- Refer to Section 8.4.6 for protocol-specific exceptions.

Definition of Unsolicited and Solicited AE

- An unsolicited AE is an AE that was not solicited using a VRC and that is communicated by a participant who has signed the informed consent. Unsolicited AEs include serious and nonserious AEs.
- Solicited AEs are predefined local (at the injection site) and systemic events for which the participant is specifically questioned, and which are noted by the participant in their VRC.

10.3.2 Definition of SAE

If an event is not an AE per definition above, then it cannot be an SAE even if serious conditions are met.

An SAE is defined as any untoward medical occurrence that, at any dose:

- Results in death**
- Is life-threatening**
 - The term “life-threatening” in the definition of “serious” refers to an event in which the participant was at risk of death at the time of the event. It does not refer to an event, which hypothetically might have caused death, if it were more severe.
- Requires inpatient hospitalization or prolongation of existing hospitalization**
 - Hospitalization is defined as an inpatient admission, regardless of length of stay, even if the hospitalization is a precautionary measure for continued observation. (Note: Hospitalization for an elective procedure to treat a pre-existing condition that has not worsened is not an SAE. A pre-existing condition is a clinical condition that is diagnosed prior to the use of an MSD product and is documented in the participant’s medical history.)

d. Results in persistent or significant disability/incapacity

- The term disability means a substantial disruption of a person's ability to conduct normal life functions.
- This definition is not intended to include experiences of relatively minor medical significance such as uncomplicated headache, nausea, vomiting, diarrhea, influenza, and accidental trauma (eg, sprained ankle) that may interfere with or prevent everyday life functions but do not constitute a substantial disruption.

e. Is a congenital anomaly/birth defect

- In offspring of participant taking the product regardless of time to diagnosis.

f. Other important medical events

- Medical or scientific judgment should be exercised in deciding whether SAE reporting is appropriate in other situations such as important medical events that may not be immediately life-threatening or result in death or hospitalization but may jeopardize the participant or may require medical or surgical intervention to prevent 1 of the other outcomes listed in the above definition. These events should usually be considered serious.

Examples of such events include invasive or malignant cancers, intensive treatment in an emergency room or at home for allergic bronchospasm, blood dyscrasias or convulsions that do not result in hospitalization, or development of drug dependency or drug abuse.

10.3.3 Additional Events Reported

Additional events that require reporting

In addition to the above criteria, AEs meeting either of the below criteria, although not serious per ICH definition, are reportable to the Sponsor.

- Is a cancer
- Is associated with an overdose

10.3.4 Recording AE and SAE

AE and SAE recording

- When an AE/SAE occurs, it is the responsibility of the investigator to review all documentation (eg, hospital progress notes, laboratory, and diagnostics reports) related to the event.
- The investigator will record all relevant AE/SAE information on the AE CRFs/worksheets at each examination.
- It is not acceptable for the investigator to send photocopies of the participant's medical records to the Sponsor in lieu of completion of the AE CRF page.
- There may be instances when copies of medical records for certain cases are requested by the Sponsor. In this case, all participant identifiers, with the exception of the participant number, will be blinded on the copies of the medical records before submission to the Sponsor.
- The investigator will attempt to establish a diagnosis of the event based on signs, symptoms, and/or other clinical information. In such cases, the diagnosis (not the individual signs/symptoms) will be documented as the AE/SAE.

Assessment of intensity/toxicity

- An event is defined as "serious" when it meets at least 1 of the predefined outcomes as described in the definition of an SAE, not when it is rated as severe.
- The investigator will make an assessment of intensity for each AE and SAE (and other reportable safety event) reported during the study and assign it to 1 of the following categories:
 - Mild: An event that is easily tolerated by the participant, causing minimal discomfort and not interfering with everyday activities (for pediatric studies, awareness of symptoms, but easily tolerated).
 - Moderate: An event that causes sufficient discomfort to interfere with normal everyday activities (for pediatric studies definitely acting like something is wrong).
 - Severe: An event that prevents normal everyday activities. An AE that is assessed as severe should not be confused with an SAE. Severe is a category utilized for rating the intensity of an event; and both AE and SAE can be assessed as severe (for pediatric studies, extremely distressed or unable to do usual activities).
- Injection site erythema/redness or swelling from the day of vaccination through Day 5 postvaccination will be evaluated by maximum size.

- The investigator will make an assessment of toxicity for each AE and SAE (and other reportable event) reported during the study. A toxicity grade will be assigned to injection-site AEs, specific systemic AEs, other systemic AEs, and vital sign (temperature) AEs as shown in the following tables. The toxicity grading scales used in this study are adapted from the “FDA Guidance for Industry: Toxicity Grading Scale for Healthy Adult and Adolescent Volunteers Enrolled in Preventive Vaccine Clinical Trials, September 2007.”

Injection-Site AE Toxicity Grading Scale

Injection Site Reaction to Study Vaccine/Placebo ^a	Grade 1	Grade 2	Grade 3	Grade 4
Injection-site AEs occurring Days 1 through 5 following receipt of study vaccine/placebo				
Pain/Tenderness	Does not interfere with activity	Repeated use of non-narcotic pain reliever >24 hours or interferes with activity	Any use of narcotic pain reliever or prevents daily activity	ER visit or hospitalization
Erythema/Redness	Size measured as B	Size measured as C or D	Size measured as E→	Necrosis or exfoliative dermatitis or results in ER visit or hospitalization
Induration/Swelling	Size measured as B	Size measured as C or D	Size measured as E→	Necrosis or ER visit or hospitalization
Other	Does not interfere with activity	Repeated use of non-narcotic pain reliever >24 hours or interferes with activity	Any use of narcotic pain reliever or prevents daily activity	ER visit or hospitalization
Any injection-site reaction that begins ≥6 days after receipt of study vaccine/placebo				
Pain/tenderness Erythema/Redness Induration/Swelling Other	Does not interfere with activity	Repeated use of non-narcotic pain reliever >24 hours or interferes with activity	Any use of narcotic pain reliever or prevents daily activity	ER visit or hospitalization

AE = adverse event; ER = emergency room; eVRC = electronic Vaccine Report Card; SAE = serious adverse event; VRC = vaccination report card.

^a Based upon information provided by the participant on the paper VRC/eVRC and verbally during VRC review. Erythema/Redness and Induration/Swelling are specific injection-site AEs with size designations of letters A through E→, based upon a graphic in the paper VRC/eVRC. Size A is not assigned a toxicity grade; however, injection-site AEs that measure size A should be reported as adverse experiences. If the participant has an ER visit or is hospitalized for any injection-site AE, that AE is to be assigned a toxicity grade of 4, regardless of the size measured.

Specific Systemic AE Toxicity Grading Scale

Systemic (General)	Mild (Grade 1)	Moderate (Grade 2)	Severe (Grade 3)	Potentially Life Threatening (Grade 4)
Headache	No interference with activity	Repeated use of non-narcotic pain reliever >24 hours or some interference with activity	Significant; any use of narcotic pain reliever or prevents daily activity	ER visit or hospitalization
Fatigue	No interference with activity	Some interference with activity	Significant; prevents daily activity	ER visit or hospitalization
Myalgia	No interference with activity	Some interference with activity	Significant; prevents daily activity	ER visit or hospitalization

ER = emergency room

Other Systemic AE Toxicity Grading Scale

Systemic Illness ^a	Mild (Grade 1)	Moderate (Grade 2)	Severe (Grade 3)	Potentially Life Threatening (Grade 4) ^b
Illness or clinical AE (as defined according to applicable regulations)	No interference with activity	Some interference with activity not requiring medical intervention	Prevents daily activity and required medical intervention	ER visit or hospitalization

ER = emergency room; eVRC = electronic Vaccine Report Card; SAE = serious adverse event; VRC = vaccination report card.

^a Based upon information provided by the patient on the paper VRC/eVRC and verbally during the eVRC review during the primary safety follow-up period. For SAEs reported beyond the primary safety follow-up period, grading will be based upon the initial report and/or follow-up of the event.

^b AEs resulting in death will be assessed as Grade 4.

Vital Sign (Temperature) Toxicity Grading Scale

Vital Signs ^a	Mild (Grade 1)	Moderate (Grade 2)	Severe (Grade 3)	Potentially Life Threatening (Grade 4)
Fever (°C) ^b (°F) ^b	38.0 to 38.4 100.4 to 101.1	38.5 to 38.9 101.2 to 102.0	39.0 to 40.0 102.1 to 104.0	>40.0 >104.0

^a Participant should be at rest for all vital sign requirements.

^b Oral temperature; no recent hot or cold beverages or smoking.

Assessment of causality

- Did the Sponsor's product cause the AE?
- The determination of the likelihood that the Sponsor's product caused the AE will be provided by an investigator who is a qualified physician. The investigator's signed/dated initials on the source document or worksheet that supports the causality noted on the AE form, ensures that a medically qualified assessment of causality was done. This initialled document must be retained for the required regulatory time frame. The criteria below are intended as reference guidelines to assist the investigator in assessing the likelihood of a relationship between the test product and the AE based upon the available information.
- **The following components are to be used to assess the relationship between the Sponsor's product and the AE;** the greater the correlation with the components and their respective elements (in number and/or intensity), the more likely the Sponsor's product caused the AE:
 - **Exposure:** Is there evidence that the participant was actually exposed to the Sponsor's product such as: reliable history, acceptable compliance assessment (diary, etc.), seroconversion or identification of vaccine virus in bodily specimen?
 - **Time Course:** Did the AE follow in a reasonable temporal sequence from administration of the Sponsor's product? Is the time of onset of the AE compatible with a vaccine-induced effect?
 - **Likely Cause:** Is the AE not reasonably explained by another etiology such as underlying disease, other drug(s)/vaccine(s), or other host or environmental factors?
 - **Rechallenge:** Was the participant re-exposed to the Sponsor's product in the study?
 - If yes, did the AE recur or worsen?
 - If yes, this is a positive rechallenge.
 - If no, this is a negative rechallenge.

(Note: This criterion is not applicable if: (1) the initial AE resulted in death or permanent disability, or (2) the study is a single-dose vaccine study; or (3) Sponsor's product(s) is/are used only 1 time.)

NOTE: IF A RECHALLENGE IS PLANNED FOR AN AE THAT WAS SERIOUS AND MAY HAVE BEEN CAUSED BY THE SPONSOR'S PRODUCT, OR IF RE-EXPOSURE TO THE SPONSOR'S PRODUCT POSES ADDITIONAL POTENTIAL SIGNIFICANT RISK TO THE PARTICIPANT THEN THE RECHALLENGE MUST BE APPROVED IN ADVANCE BY THE SPONSOR CLINICAL DIRECTOR, AND IF REQUIRED, THE IRB/IEC.

- **Consistency with study intervention profile:** Is the clinical/pathological presentation of the AE consistent with previous knowledge regarding the Sponsor's product or drug class pharmacology or toxicology?
- The assessment of relationship will be reported on the CRFs/worksheets by an investigator who is a qualified physician according to his/her best clinical judgment, including consideration of the above elements.
- Use the following scale of criteria as guidance (not all criteria must be present to be indicative of a Sponsor's product relationship).
 - Yes, there is a reasonable possibility of Sponsor's product relationship:
 - There is evidence of exposure to the Sponsor's product. The temporal sequence of the AE onset relative to the administration of the Sponsor's product is reasonable. The AE is more likely explained by the Sponsor's product than by another cause.
- No, there is not a reasonable possibility of Sponsor's product relationship:
 - Participant did not receive the Sponsor's product OR temporal sequence of the AE onset relative to administration of the Sponsor's product is not reasonable OR the AE is more likely explained by another cause than the Sponsor's product. (Also entered for a participant with overdose without an associated AE.)

- For each AE/SAE, the investigator must document in the medical notes that he/she has reviewed the AE/SAE and has provided an assessment of causality.
- There may be situations in which an SAE has occurred and the investigator has minimal information to include in the initial report to the Sponsor. However, it is very important that the investigator always make an assessment of causality for every event before the initial transmission of the SAE data to the Sponsor.
- The investigator may change his/her opinion of causality in light of follow-up information and send an SAE follow-up report with the updated causality assessment.
- The causality assessment is 1 of the criteria used when determining regulatory reporting requirements.

Follow-up of AE and SAE

- The investigator is obligated to perform or arrange for the conduct of supplemental measurements and/or evaluations as medically indicated or as requested by Sponsor to elucidate the nature and/or causality of the AE or SAE as fully as possible. This may include additional laboratory tests or investigations, histopathological examinations, or consultation with other health care professionals.

- New or updated information will be recorded in the CRF.
- The investigator will submit any updated SAE data to the Sponsor within 24 hours of receipt of the information.

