8.4.8.1 Solicited Adverse Events

Solicited AEs for this study are summarized in [Table 6](#).

Table 6 Solicited Adverse Events for V116-001

Type of Solicited Adverse Event	Predefined Solicited Adverse Events	Solicited Time Period
Injection site	
• Injection-site tenderness/pain• Injection-site redness/erythema• Injection-site swelling	Day 1 to Day 5 postvaccination
Systemic	
• Headache• Muscle pain/myalgia• Joint pain/arthralgia• Tiredness/fatigue	Day 1 to Day 5 postvaccination

All solicited injection-site AEs will be considered related to study intervention. The investigator will assess all solicited injection-site AEs for toxicity, and all solicited systemic AEs for both toxicity and causality (Appendix 3).

In addition, the investigator will review all solicited AEs for the following:

- Is the event a symptom of another diagnosis?
- Is the event ongoing at the end of the solicited period?
- Does the event meet serious criteria?

A solicited AE that meets any of the above criteria must also be reported on the appropriate eCRF as specified in the data entry guidelines.

Phase 1:

Solicited injection-site AEs and solicited systemic AEs reported by the participant using the paper VRC will be entered by study site personnel on the appropriate eCRF.

Phase 2:

Solicited injection-site AEs and solicited systemic AEs reported by the participant using the eVRC will be transferred directly to the Sponsor database.

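### Does the missing joint-pain row, and a fallback toxicity scale with two unmatched cases, call for a change to the plan?

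*Combined protocol and SAP*

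**What the plan says.** Table 6 in Section 8.4.8.1 predefines four systemic events for Days 1 to 5: headache, muscle pain, "Joint pain/arthralgia" and tiredness. The same section has the investigator assess "all solicited systemic AEs for both toxicity and causality".

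Section 10.3.4 states how: "A toxicity grade will be assigned to injection-site AEs, specific systemic AEs, other systemic AEs", and temperature events likewise, using the tables that follow. The Specific Systemic scale has three rows (headache, fatigue, myalgia). The Other Systemic scale has one general row for an illness or clinical adverse event. Its Grade 2 cell is "Some interference with activity not requiring medical intervention" and its Grade 3 cell is "Prevents daily activity and required medical intervention". An emergency room visit or hospitalization is Grade 4, and a footnote makes death Grade 4.

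Section 10.3.4 also requires a separate intensity rating for each event, in three categories. The top one begins "Severe: An event that prevents normal everyday activities" and does not mention medical intervention.

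**The concern.** Two things look wrong. First, a solicited event that must be graded has no row of its own, and no sentence says which table governs it. Second, the table it falls to has gaps. A participant kept from normal activities by joint pain who seeks no care fits neither Grade 2 nor Grade 3. The same limitation reported as myalgia or fatigue meets "Significant; prevents daily activity" and is Grade 3. The wording also sits badly with the intensity definition of Severe, which depends on activity alone.

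At stake would be the completeness and comparability of toxicity grades for one solicited event, and for any unsolicited systemic event graded on the same row, in a first-in-human study whose safety and tolerability data go to the standing internal data monitoring committee.

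**Working it through.** The plan gives no figure to reproduce here, so the check is a count from the tables followed by a search for where toxicity grade is used.

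**Rows.** Solicited systemic events: 4. Rows in the Specific Systemic scale: 3. Without a row: 4 − 3 = 1 (joint pain).

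**Cells.** Three levels of activity limitation × two states of medical intervention = 6 combinations, leaving out emergency room visits, hospitalization and death, which are Grade 4.

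| Activity | Medical intervention | Other Systemic scale, read literally | Myalgia or fatigue row | Intensity rating |
|---|---|---|---|---|
| No interference | No | 1 | 1 | Mild |
| No interference | Yes | 1 | 1 | Mild |
| Some interference | No | 2 | 2 | Moderate |
| Some interference | Yes | no match | 2 | Moderate |
| Prevented | No | no match | 3 | Severe |
| Prevented | Yes | 3 | 3 | Severe |

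So 2 of 6 are unmatched on the Other Systemic scale and 0 of 6 on the myalgia and fatigue rows. The 2 treats Grade 1 as silent on intervention, which is how it is written; if Grade 1 were taken to imply none, the count would be 3 of 6. These are logical cells, not participants. The document gives no rate for how often either case would arise.

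**Comparison with the other rows.** Seven rows grade by effect on activity: three for injection-site reactions (pain on Days 1 to 5; other reactions on Days 1 to 5; all reactions from day 6, counted as one), headache, fatigue, myalgia, and the Other Systemic row. In the three injection-site rows, Grade 3 is "Any use of narcotic pain reliever or prevents daily activity", with no further qualifier. Headache, fatigue and myalgia put the word Significant in front. If that word only describes, prevented activity alone gives Grade 3 in 3 + 3 = 6 of 7 rows; if it is a condition, in 3 of 7. On either reading, only the Other Systemic row ties Grade 3 to medical intervention.

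**Is there a way to grade the two unmatched cases?** The Other Systemic columns are headed Mild (Grade 1), Moderate (Grade 2) and Severe (Grade 3). The intensity categories carry the same three names under the same heading on intensity and toxicity, and the last column of the table shows that they cover all six combinations. Some interference with intervention is Moderate, and prevented activity without intervention is Severe. Each points to one column of the toxicity table. The cell text is imperfect, but the investigator is not left without guidance.

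**Where is toxicity grade used?**

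- Section 9.4.3 and Table 9: the solicited-event endpoints are proportions of participants with the event. Joint pain is prespecified as Tier 2 and analysed by occurrence with a Miettinen and Nurminen interval.
- Section 9.6.3: events not prespecified are assigned to a tier by whether at least 4 participants in a group had the event. Grade plays no part.
- Section 4.4.1: early termination refers to incidence and severity, not to toxicity grade.
- Sections 4.1, 4.2, 9.7 and 10.1.4.1: committee review and dose selection refer to safety, tolerability and immunogenicity data, not to toxicity grade.
- Section 8.1.13: before emergency unblinding the investigator should try to chart intensity and toxicity grade, but unblinding is not to wait for it.

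No planned estimate, interval or stated decision rule takes the grade as an input.

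**The case for a change.** The best case for acting is that intensity and toxicity are two separate required assessments, so a complete intensity scale does not fill a hole in the toxicity scale. Section 8.1.13 names them side by side, which supports that. Without an explicit convention, two investigators could give identical joint pain different grades, and grading tables exist to prevent this. Where Appendix 3 means to leave an event ungraded, as for the smallest injection-site size category, it says so; silence here is therefore not an exemption. The repair would be cheap: one row and some wording.

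Much of this stands. The wording is untidy, and a descriptive table of joint pain by toxicity grade could be less consistent than one for myalgia. Two parts do not stand. It is too strong to say that the rule cannot be applied: the general row is there for systemic events not named in the specific table, and its column labels lead to definitions without the gap. Nor is loss of comparability particular to joint pain, since headache already carries pain-reliever criteria that fatigue and myalgia lack. The stake in committee review is a possibility only. The content of that review is left to a charter, severity is available from the complete intensity scale, and nothing suggests that grading would differ between blinded groups.

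**Conclusion.** The counts are right: 1 of 4 solicited systemic events has no specific row, and 2 of 6 combinations have no literal match on the scale it falls to. This is a wording gap that investigators and data managers can fill from the definitions in the same section, and closing it would change no planned result. The proportions with solicited events, the Tier 2 intervals, tier assignment and sample size are all untouched, and each event is still recorded and rated for intensity.

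The conclusion rests on three points: that joint pain belongs on the Other Systemic scale, which is an inference by elimination; that investigators read the column labels with the intensity definitions of the same name; and that no document outside the protocol, such as the supplemental analysis plan or the committee charter, makes a decision depend on toxicity grade. The data entry guidelines may already hold a convention, but they are not available to check. The sponsor could align Table 6, the two systemic scales and the intensity definitions if Appendix 3 is reopened for another reason. The plan does not need an amendment for this.
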